### **Subgroup analyses**

Subgroup analyses (separately for the two populations) will explore the effect on prolapse symptoms at 12 months after surgery of:

- mesh kit versus other procedures in those that could have been randomised to mesh kits
- concomitant continence procedure or not
- concomitant hysterectomy/cervical amputation/vault procedure or not
- age (<60 or >=60 years)

- parity
- between those having one type of prolapse repair alone (anterior or posterior) versus both

Heterogeneity of treatment effects amongst subgroups will be tested for using the appropriate subgroup by treatment group interactions. Stricter levels of statistical significance ( $2P < 0.01$ ) will be sought, reflecting the exploratory nature of these analyses.

### **Non-compliance will allocated treatment**

The primary analysis strategy of the trial will follow the intention-to-treat principle, i.e. participants will analysed as randomised, regardless of the intervention received. However, secondary analyses may be undertaken to investigate issues relating to compliance (e.g. mesh inlays being misidentified as mesh kits). Depending on levels and patterns of non-compliance analyses methods other than intention-to-treat may be used, for example per-protocol analyses or estimation of complier average treatment effects.

### **Methodological analyses**

The responses from women and their objective clinical findings will provide a rich data source for exploration of the correlation between patient-reported and clinician-observed outcomes, and between prolapse symptoms and their effect on quality of life. This methodological research is intended to advance the controversial field.

#### **1.1. Timing of analyses**

An analysis of 12 month outcomes (including the primary outcome) will be performed and published one year after recruitment closes. A final analysis of all outcomes will be conducted at the end of the trial when all follow-up has been completed (up to 24 months).

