5. DATA COLLECTION AND PROCESSING

Follow up will continue for 24 months from the date of operation. It is not part of this protocol or the current study to follow up the women beyond this time. However, consent will be sought to make this possible in the future, and long term follow up is planned (Appendix IV).

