5.1 Questionnaires

Women will be asked to complete a baseline questionnaire before surgery. Follow up questionnaires will be sent by post at 6, 12, 18 and 24 months after surgery. Content will include:

i) Prolapse symptoms (POP-SS,⁷)

- ii) Urinary outcome questions (urinary symptoms and urinary leakage, effect on QOL, http://www.iciq.net/), pad use, catheter use)
- iii) Bowel function outcome questions and effect on QoL
- iv) Sexual function and vaginal symptoms, effect on QoL (http://www.iciq.net)
- v) Health care utilisation questions
- vi) Exercise, weight and height, including pelvic floor exercises
- vii) EQ 5D¹²

and additionally at baseline only:

- i) Obstetric history
- ii) GP address and phone number
- iii) 'Best Contact' at another address for follow up (not wife or partner)
- iv) Other medical problems
- v) Date of operation

Postoperatively within a week of surgery:

- i) infection / pyrexia
- ii) pain and pain relief
- iii) blood transfusion
- iv) vaginal pack
- v) urinary catheter and recatheterisation
- vi) bowel function (need for laxatives)
- vii) complications and return to theatre
- viii) length of stay

At 12 months after surgery (randomised women only):

ii) clinical findings

At 18 months only:

i) Participant Unit Cost Questionnaire

At 6, 12 and 24 months:

- i) Complications
- ii) Need for further treatment for prolapse
- iii) Further treatment for prolapse received or planned, use of health services

Theatre findings and procedures will be recorded in the BSUG database, using a questionnaire designed to be compatible with the requirements of both BSUG and PROSPECT.

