6.3 Statistical analysis

A single principal analysis is anticipated at 12 months after the last woman is recruited. The Data Monitoring Committee will determine the frequency of confidential interim analyses, but at present these are planned on four occasions during the data collection period.

All analyses within the RCT will be based on the intention-to-treat principle. All outcomes in both trials will be described with the appropriate descriptive statistics where relevant: mean and standard deviation for continuous and count outcomes, or medians and inter-quartile range if required for skewed data, numbers and

percentages for dichotomous and categorical outcomes (for example subjective recurrence of prolapse).

Analysis of the primary outcome (POP-SS) will estimate the mean differences (and 95% confidence interval) between the intervention and control groups using a general linear model that adjusts for the minimisation covariates and other important prognostic covariates, including the baseline symptom score, at 12 months after surgery. A similar analysis will be used to analyse the primary outcome at 6 and 24 months.

All secondary analyses will be analysed in a similar manner but using the appropriate generalised linear model (for example logistic regression for dichotomous data such as subjective prolapse failure, Poisson or negative binomial regression for count data such as number of nights in hospital) or time to event methods (e.g. Cox regression on time to further surgery) where required. We will explore analysing outcomes at all time points simultaneously using for example, Generalised Estimating Equations or Generalised Linear Latent and Mixed Models, and relevant link functions, to explore changes in outcome over time.

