7. RECRUITMENT RATES AND MILESTONES

7.1 Recruitment rates

Figure 1 shows the projected recruitment of centres and participants, and projected number of women to be approached. Three centres will be established relatively early in the project (by three months) followed by roll out to the others over the subsequent 15 months.

The participant recruitment graph in Figure 1 has been modelled to take into account: the phased rollout to the centres over the first 18 months; that there will be lags between the approach to women when they are in hospital for pre-assessment and their admission for operation; and that there are likely to be fewer operations around August and over Christmas (due to holidays). Randomisation continues after the final recruitment because of these 'lags'.

[figure not shown]

In summary, we aim to recruit around 2250 women to the randomised trials, and a further 2250 to the non-randomised Comprehensive Cohort. This amounts to 300 women per centre (15 sites) over an average recruitment period of 18 months, half of whom will be randomised.

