The Surgery for Prolapse Cochrane Review was updated in 2013.³ The review authors found 22 trials of mesh in prolapse surgery (3 used absorbable synthetic mesh; 7 used biological mesh; 12 used non-absorbable mesh). The data on biological mesh were at best conflicting, while women had both fewer symptoms and less objective prolapse after non-absorbable mesh at one year after surgery. However, few of the trials reported outcomes at two years or more, reporting of complications was sparse and none differentiated between primary and secondary repairs. Therefore, the overall benefits and costs of mesh in prolapse surgery remain undetermined. The Cochrane Review further identified the lack of long term follow-up data as a serious limitation.

The importance of long term follow-up has also been highlighted in the literature by the gynaecology community⁴ and NICE.⁵ Furthermore, lack of long term follow-up has been highlighted by NICE as a discussion point when counselling the patient for POP surgery. Long term follow-up of all of the PROSPECT participants is therefore necessary to inform health-care commissioners, health-care professionals and consumers alike. Such long term follow up will establish the (anticipated) benefits of mesh versus the likelihood of adverse effects such as mesh exposure, which may occur many years later.²

Methods

The PROSPECT participants will be contacted at 2-yearly intervals starting at 4 years after surgery and continuing to 14 years after surgery (6 questionnaires in total). For those women who were recruited into PROSPECT but who never received a prolapse operation as part of the trial, questionnaires will be issued at 2-yearly intervals starting at 4 years post-randomisation and continuing to 14 years post-randomisation. Woman who did not consent to be contacted in the future for long term follow-up or who had previously withdrawn from PROSPECT will be excluded from the long term follow-up study.

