## Primary Outcomes

The primary patient-reported outcomes are symptoms of prolapse, measured as:

- the number and frequency of prolapse symptoms on the Pelvic Organ Prolapse Symptom Scale (POP-SS) at one year after surgery
- a quality of life outcome measured as the overall effect of prolapse symptoms on everyday life.

The POP-SS is a composite outcome measure comprising seven patient recorded items each relating to a different symptom. Each item has an ordinal response schedule with five levels of response based on frequency of the symptom (“never”, “occasionally”, “sometimes”, “most of the time” and “all of the time”) and is scored from 0 to 4 respectively. The overall POP-SS score is the sum of each item score and can range from zero to 28.

For the primary analysis, individual items that are missing will be assumed to have a value of zero. However, this assumption will be tested in sensitivity analyses. If all seven questions are unanswered, then the POP-SS score will be treated as missing.

The primary economic outcome measure of cost effectiveness is incremental cost per QALY (QALYs based on the EQ-5D). The cost effectiveness analysis is set out separately in the economic analysis plan.

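### The 12-month analysis is timed from the close of recruitment, with no time allowed for surgery-timed questionnaires to come back, and the 12-month point is undefined for randomised women who never have surgery

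*SAP*

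**What the plan says.** The SAP (Primary Outcomes) and Protocol 6.2 both set the primary outcome as POP-SS one year after surgery. The score comes from a postal questionnaire, which Protocol 5.1 runs on the same clock: "Follow up questionnaires will be sent by post at 6, 12, 18 and 24 months after surgery". Protocol 5 agrees: "Follow up will continue for 24 months from the date of operation".

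The analysis is on a different clock. The SAP (Timing of analyses, numbered 1.1) says: "An analysis of 12 month outcomes (including the primary outcome) will be performed and published one year after recruitment closes". Protocol 6.3 says: "A single principal analysis is anticipated at 12 months after the last woman is recruited". The SAP then plans a further analysis of all outcomes when 24-month follow-up is finished. Protocol 7.1, explaining the original recruitment projection, allows for a wait between approaching a woman and her admission, and adds: "Randomisation continues after the final recruitment because of these" lags.

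Elsewhere a third clock appears. Protocol 6.5.1 times the health care utilisation questionnaire from randomisation, and the 12-month follow-up milestones in Protocol 7.3 and 7.4 also count from randomisation.

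Women without surgery are mentioned only in the Methods of Appendix IV: "For those women who were recruited into PROSPECT but who never received a prolapse operation as part of the trial". They are sent questionnaires counted from randomisation, but only from year 4. The SAP (General Methods) analyses every woman as randomised.

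**The concern.** A woman operated on the day recruitment closes reaches her 12-month date on the day the result is meant to be already in print. Her questionnaire has still to be posted, completed, returned and, if she is slow, chased. The timing sentence therefore cannot be obeyed without leaving out some late returns, and any wait for surgery adds to them. The SAP's Loss to follow-up section recognises only complete and partial loss. It has no category for a score that is not yet due or not yet back, so such a score would be treated as missing, on top of the 15% dropout already allowed for. The later final analysis would pick these scores up, but it would then give a second estimate of a primary outcome that had already been published.

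The second gap concerns the meaning of the outcome itself. One year after surgery is not a date for a woman who has no surgery. If the surgery clock is applied to her, she is sent no 12-month POP-SS and contributes nothing to an analysis described as intention-to-treat.

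**Working it through.** **The plan's own timetable.** Protocol 7.4 closes recruitment by month 42 and completes 12-month follow-up by month 54: 42 + 12 = 54. The original timetable in 7.3 does the same: 30 + 12 = 42. Both reproduce exactly, so the allowance for surgery wait, questionnaire return and data cleaning is zero.

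**Calendar check.** The SAP closes recruitment in August 2013, so its 12-month result is due in print in August 2014. Appendix IV describes the retention system already used in the trial: a first reminder three weeks after an unreturned questionnaire, then a further postal or telephone reminder. A last operation in August 2013, plus 12 months, plus three weeks, reaches about September 2014.

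**Women affected.** Women affected = monthly accrual × delay.

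- Accrual, lower: 1353 randomised from January 2010 to August 2013 (Appendix IV), 44 months; 1353/44 = 30.75 per month.
- Accrual, upper: 70 per month, the projection in Protocol 2.7.3.
- Delay: not given in the documents. Assumed to be three weeks (21/30.4 = 0.69 month) or one month.

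Three weeks: 30.75 × 0.69 = 21 and 70 × 0.69 = 48; divided by 1353, 1.6% to 3.6%. One month: 31 to 70, or 2.3% to 5.2%. These are upper figures at each rate, because women who reply promptly are counted too. In the secondary trial, 155/44 = 3.5 women per month, or 2.3% of 155 for each month of delay.

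**Power.** Inputs: difference 2, SD 8 and alpha 0.025 (taken as two-sided) from the SAP's sample size section; 15% dropout; arms pooled from SAP Table 2 as the SAP pools them. Standard v synthetic is 253 + 178 = 431 against 256 + 181 = 437. Standard v biological is 253 + 116 = 369 against 255 + 114 = 369. With f the fraction lost to timing and each arm multiplied by 0.85 × (1 − f), power = Φ(2 / (8 × √(1/n1 + 1/n2)) − 2.241).

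| Delay | Standard v synthetic | Standard v biological |
|---|---|---|
| None | 87.6% | 81.3% |
| 3 weeks | 87.0% to 86.3% | 80.6% to 79.8% |
| 1 month | 86.8% to 85.7% | 80.3% to 79.0% |

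The loss at one month is 0.8 to 1.9 points for synthetic mesh and 1.0 to 2.3 points for biological mesh.

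**Women without surgery.** No arithmetic settles this, because their number is not given. For scale, each 1% is 13.5 women in the primary trial and 1.6 in the secondary trial. Side by side, Protocol 5, 5.1 and 6.2 count from surgery, 6.5.1, 7.3 and 7.4 count from randomisation, and Appendix IV gives a rule only from year 4. None gives these women a POP-SS date at 12 months.

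**The case against.** A reader might infer that the plan deliberately truncates the last women's data. The documents do not support that. No data cut-off is set, Protocol 6.3 only anticipates the timing, and the SAP's final analysis would take in late scores.

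A reader might also assume a wait of several months between recruitment and surgery, since Protocol 2.7.3 names waiting time as a cause of delay, and so reach a much larger loss. Protocol 2.3 puts randomisation on the morning of surgery or the afternoon before, and the revised text treats recruited and randomised as the same thing (compare 7.2 with 7.4). The lag in 7.1 belongs to the original projection. On that reading little remains beyond the reminder period. The rate of 70 per month is also a projection: 1450 women were planned by month 42, and 1353 were randomised by August 2013.

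The month 68 milestone for completed analysis is no contradiction either. It follows the end of 24-month follow-up at month 66 and belongs to the final analysis.

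On women without surgery, it is tempting to say that they have no follow-up at all, or that the loss depends on allocation because mesh was unavailable. Protocol 2.6 promises active follow-up of all women in the RCTs, and two sections count from randomisation, so the anchor is inconsistent rather than absent. Mesh unavailability is handled before allocation by leaving that arm off the menu (Protocol 3.1; SAP Study Design).

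All of this stands, and it makes the point smaller. It does not provide time for the last questionnaires to come back, and it does not give women without surgery a 12-month date.

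**Conclusion.** The point holds in a limited form. The timing sentences in the SAP and Protocol 6.3 leave no slack and, taken literally, force the first published analysis to omit late returns. The size rests on an assumed delay of three weeks to one month and on accrual between the achieved average and the projection: about 1.6% to 5.2% of the primary trial before prompt responders are removed, and about 1 to 2 points of power at one month. Arms accrue side by side, so a calendar effect of this kind should fall about equally on them; no bias between arms is evident.

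The undefined 12-month point for women without surgery is a separate defect of definition. Its size cannot be worked out from the documents, and randomising within a day of theatre should keep it small. It still needs a rule, because an analysis of all women as randomised needs one time zero that every woman has.

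**What to change.** 1. In the SAP (Timing of analyses) and Protocol 6.3, replace the timing sentences with a statement that the 12-month analysis starts when the last randomised woman's 12-month questionnaire and its reminder period have closed and the 12-month data are locked. The first published estimate of the primary outcome is then made on complete 12-month data.
2. In Protocol 5 and 5.1 and in the SAP, state that a randomised woman who has no operation is sent the follow-up questionnaires timed from randomisation, and is analysed at those times under intention-to-treat. This brings the Appendix IV rule forward to the main study.

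The cost is a few sentences, a few extra postal questionnaires and a short delay to the first publication. Sample size and model are unchanged.

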## Sample Size and Power Calculation

In an average population of women having prolapse surgery, about 70% will be having a primary procedure. Two comparisons will be made:

- a standard repair versus a standard repair using a biological graft inlay; and
- a standard repair versus a standard repair using a non-absorbable or combined mesh inlay.

Pilot data have shown that a conservative estimate of the standard deviation of the primary patient-reported outcome POP-SS is 8 units. A difference in means of 2 units would represent an improvement in the response to a POP-SS question, for example, a feeling of something coming down or in the vagina, from 'Most of the Time' to 'Occasionally'. To detect a standardised difference of 0.25 with 90% power and alpha equal to 0.025 (to maintain the nominal p value at 0.05 with two tests being used), we would need to randomise 400 women to each arm of the study. Best efforts using evidence based techniques will be employed to maximise the response rate at follow up. Nevertheless, we feel it prudent to inflate the estimated sample size for 15% dropout at one year requiring approximately 1450 women having primary surgery to be recruited to the trial. Adjusting for baseline covariates and minimising the loss to follow up will potentially improve this power. A trial of this size would also be adequately powered to detect important differences in the economic and secondary outcomes.

It is estimated that the other 30% of women requiring anterior and/or posterior repair will receive a secondary or subsequent repair. Therefore, during the proposed time period required for recruiting 1450 women to the primary repair RCT above, it is anticipated approximately 620 women having secondary surgery will be eligible and will be willing to be randomised. Within the secondary RCT two comparisons will be made:

- a standard repair versus a standard repair using a non-absorbable or combined mesh inlay; and

- a standard repair versus a mesh kit procedure.

It would be possible to detect with 90% power and alpha equal to 0.025 a standardised effect size of 0.38 which equates to 3 points on the POP-SS scale (this estimated effect detectable has been calculated adjusting for potential 15% dropout at one year). The pilot data from IMPRESS indicated that women having secondary repairs have a higher level of symptoms at baseline. Therefore it is biologically plausible that these women may show a larger benefit from the options available.

Thus 2070 women will be randomised in total. Based on data from the feasibility study, we expect that in a typical centre, 200 women a year will be eligible, of whom 50% will be willing to be randomised. Of these women, 70% will be having primary surgery, 30% will have both anterior and posterior surgery, 15% may have a concomitant continence procedure and 30% a concomitant upper vaginal procedure (e.g. cervical amputation or vaginal hysterectomy). More than 15 centres are willing to take part.

If we conservatively assume 50% of the women will agree to be randomised, we calculate we will need the equivalent of 18 months full time recruitment to randomise 2070 women and will follow up 4140 women in total including those in the Comprehensive Cohort. Allowing for about another 10% who will not wish to be studied in any way, we will need to approach around 4500 women.

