2.7.3 Recruitment extension

Various issues caused delays in establishing the study at many participating sites, with the supply of mesh, delay in establishing research nurse support and the waiting time for surgery being the main issues. Therefore an extension to the recruitment phase of the trial is necessary to achieve the required recruitment targets.

1. Primary repair RCT

At steady state, the recruitment rate was assumed to be approximately 84 primary repair women per month. However recruitment to the primary repair trial has been slower than anticipated.

The revised projections for the extension period are based on a moving average from the previous two months (October and November 2011), resulting in an expected mean recruitment figure of 70 primary repair women per month (1.9 women per centre per month). Allowing for a staggered start for the remaining centres (37 in total), a 12 month extension will be required to reach the originally specified sample size.

2. Secondary repair RCT

It was estimated that 30% of the women screened during PROSPECT would be having a secondary or subsequent repair. Therefore, during the proposed time period for randomising 1450 women to the primary repair trial, it was anticipated that approximately 620 women having secondary surgery would also be randomised. However recruitment to the secondary repair arm has been lower than expected. The main reason for this is that a secondary repair in PROSPECT is defined as a

recurrence of prolapse after a previous procedure, when the recurrence is in the **same** compartment. An analysis of the first 1000 women recruited to PROSPECT indicated that approximately 16% of women meet this criterion. As a result there are fewer women than expected who are eligible for the secondary repair trial (16% compared with the anticipated 30%).

Although a 12 month extension will not be sufficient in terms of achieving the original recruitment target for this RCT, it is anticipated that 174 women will be randomised.

3 TRIAL INTERVENTIONS (Operations and Standard Operating procedures)

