APPENDIX IV LONG TERM FOLLOW-UP

Background

PROSPECT (PROlapse Surgery, Pragmatic Evaluation by randomised Controlled Trial) is the largest randomised controlled trial conducted to date of the use of mesh in women having prolapse surgery. It addresses the use of no mesh, a biological mesh inlay, and a nonabsorbable mesh inserted as an inlay or used in a kit; and separately in women having their first prolapse operation or repeat surgery.

PROSPECT recruited 3091 women from 35 centres across the UK between January 2010 and August 2013. There were two trials, one amongst women having their first prolapse operation (Primary trial, where 1353 women were randomised to no mesh, non-absorbable mesh inlay or biological mesh inlay); and those having repeat surgery (Secondary trial, where 155 women were randomised to no mesh, non-absorbable mesh inlay or mesh kit). Women who were not eligible for randomisation were enrolled into the Comprehensive Cohort (1583 women). The following information was collected:

- Demographic and surgical information at recruitment and at operation;
- Patient reported outcome data (prolapse symptoms, urinary, bowel and sexual function and EQ-5D) through questionnaires at 6, 12 and 24 months;
- Randomised women were examined 12 months after surgery to identify treatment success and adverse effects;
- Information about complications, readmissions, reoperations and costs.

Within the main PROSPECT trial short term failure (within two years of the prolapse operation) was captured. However, as prolapse is a progressive and relapsing condition, with surgery having a high failure rate¹ (repeat surgery occurs on average 12 years later) it is essential to capture the long term failure in order to truly evaluate the potential benefits of mesh versus its adverse effects, which may also occur many years later.² In addition, there is very little information about the long term effects of this condition on urinary, bowel and sexual function,

Current evidence

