## **Statistical Methods**

### **General Methods**

The statistical analysis of the RCTs will be based on all women as randomised, irrespective of subsequent compliance with the treatment allocated (intention to treat). The principal comparisons will be:

- In women having a primary prolapse repair,
  - a standard anterior and/or posterior repair will be compared with a standard repair using a biological graft inlay; and
  - a standard anterior and/or posterior repair will be compared with a standard repair using a non-absorbable or combined mesh inlay.
- In women having a secondary prolapse repair,
  - a standard anterior and/or posterior repair will be compared with a standard repair using a non-absorbable or combined mesh inlay; and
  - a standard anterior and/or posterior repair will be compared with a mesh kit procedure using an introducer device.

The two trials are being considered independently because different surgical options are considered to be appropriate for clinical reasons. Women who are not randomised but who are in the Comprehensive Cohort group will be analysed according to the operation actually carried out.

Descriptive statistics will be tabulated by treatment allocation for all outcomes (mean and SD for continuous data, proportions for binary data). Treatment effects will be estimated with 95% confidence intervals for all outcomes (mean differences for continuous data, odds ratios for binary data). Statistical significance will be at the 5% level and corresponding confidence intervals will be derived. Analyses will be conducted using SAS v9.3.

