**Table 2: Number of participants randomised to each stratum in the primary RCT**

Stratum	Standard repair (A)	Synthetic mesh (B)	Biological mesh (C)
RCT1	253	256	255
RCT1B	178	181	n/a
RCT1C	116	n/a	114

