**Table 3: Number of participants randomised to each stratum in the secondary RCT**

Stratum	Standard repair (A)	Synthetic mesh (B)	Mesh kit (C)
RCT2	24	24	44
RCT2B	31	28	n/a
RCT2D	1	n/a	3

In the primary RCT, RCT1 will be analysed on its own and treatment effects for treatments B and C (compared with A) will be estimated. In addition, the RCT1 and RCT1B strata will be combined (using just data in arms A and B) in a separate model to create a further estimate of the treatment effect between A and B. Similarly, the RCT1 and RCT1C strata will be combined (using just data in arms A and C) in a separate model to create a further estimate of the treatment effect between A and C. Where strata are combined, the stratum variable will be fitted as a fixed effect in the model. The secondary trial will be similarly analysed, although RCT2 will not be combined with RCT2D due to the small number randomised to RCT2D.

Secondary outcomes will be analysed in a similar fashion to the primary outcome using appropriate link functions.

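### The SAP's power section still gives 90% power from about 620 secondary-repair women, although its own Table 3 shows 155 randomised and neither document restates what that trial can detect

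*SAP*

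**What the plan says.** The SAP section on sample size and power expects about 1450 primary-repair and 620 secondary-repair women and concludes "Thus 2070 women will be randomised in total". It sets "alpha equal to 0.025 (to maintain the nominal p value at 0.05 with two tests being used"). For the secondary trial it claims 90% power to detect "a standardised effect size of 0.38 which equates to 3 points on the POP-SS scale", after allowing for 15% dropout. Protocol 2.7.2 has the same text, and Protocol Table 1 shows the per-arm numbers behind it: 175 evaluable, 206 with dropout.

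The SAP postdates recruitment. Its Study Design section describes the position at close of recruitment in August 2013, and two tables give the final allocation: Table 2 ("Number of participants randomised to each stratum in the primary RCT") and Table 3 ("Number of participants randomised to each stratum in the secondary RCT").

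Protocol 2.7.3 accepts that the 12-month extension will not reach the secondary target, and says "it is anticipated that 174 women will be randomised"; sections 7.2 and 7.4 repeat that number. Protocol Appendix IV reports the outcome: "where 155 women were randomised to no mesh, non-absorbable mesh inlay or mesh kit". None of these places gives a revised power or detectable difference for the secondary trial at 12 months. Appendix IV does recalculate power, but only for long-term follow-up of the primary trial.

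**The concern.** One current document gives two incompatible sizes for the secondary trial, 620 and 155, a four-fold gap. The power statement belongs to the larger number and is not marked as superseded.

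The secondary trial has two of the four principal comparisons, including the study's only randomised test of mesh kits. If either is non-significant, a reader who turns to the SAP will find 90% power for 3 points next to it and may conclude that a 3-point difference has been excluded. Protocol 1.1 makes this easier by describing the whole study, introducer systems included, as adequately powered.

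**Working it through.** **Inputs.** From the SAP sample size section: SD 8; 3 points (secondary) and 2 points (primary); alpha 0.025 per comparison; 15% loss. Sidedness is not stated; two-sided is used because it reproduces the plan's 400 per arm (one-sided gives 337). Counts come from SAP Tables 2 and 3, combined as the SAP's Primary/Secondary Outcomes section prescribes (RCT2D is not pooled).

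**Formulas** (normal approximation, no covariate adjustment):
- n per arm = 2 × (2.241 + 1.282)² / d², where d is the standardised difference
- S = √(1/n₁ + 1/n₂), with n = 0.85 × number randomised
- power = Φ(difference / (SD × S) − 2.241)
- difference detectable at 90% power = SD × 3.523 × S

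**The plan's own figures reproduce.**
- Primary: 2 × 3.523² / 0.25² = 397.2, so 398 per arm against the stated 400.
- Secondary: 620 × 0.85 / 3 = 175.7 per arm. With 175, the detectable difference is 3.523 × √(2/175) = 0.377 SD, or 3.0 points. Power at 0.38 SD is 90.7%.

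**Totals actually randomised.**
- Table 2: 253 + 256 + 255 + 178 + 181 + 116 + 114 = 1353.
- Table 3: 24 + 24 + 44 + 31 + 28 + 1 + 3 = 155.

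Both agree with the totals printed in Protocol Appendix IV.

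**Secondary trial, 3 points, SD 8, alpha 0.025, 15% loss.**

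| Comparison | Randomised | Analysed | S | Power | Detectable at 90% |
|---|---|---|---|---|---|
| Standard v mesh inlay (RCT2 + RCT2B) | 24+31 = 55 v 24+28 = 52 | 46.75 v 44.2 | 0.2098 | Φ(1.787 − 2.241) = 32.5% | 5.9 points |
| Standard v mesh kit (RCT2) | 24 v 44 | 20.4 v 37.4 | 0.2752 | Φ(1.362 − 2.241) = 19.0% | 7.8 points |

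The SAP also plans to analyse RCT2 alone. There, standard v inlay is 24 v 24 and has about 15% power. Even the forecast 174 women, split equally, would have given about 35%.

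**Sensitivity, 15% loss retained.** The SAP's General Methods section uses a different level ("Statistical significance will be at the 5% level and corresponding confidence intervals will be derived"), and Protocol Appendix IV uses SD 7, so both are tried:

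| Assumptions | Mesh kit | Mesh inlay |
|---|---|---|
| SD 8, alpha 0.05 | 27.5% | 43% |
| SD 7, alpha 0.025 | 25% | 42% |
| SD 7, alpha 0.05 | 34% | 53% |

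With no loss at all, SD 8 and alpha 0.025 give 22% and 38%.

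**Expected precision.** With SD 8 and 15% loss, the half-width of a 95% confidence interval is 1.96 × 8 × S: 3.3 points for the inlay comparison and 4.3 points for the kit comparison. Both exceed 3 points, so an observed difference of zero would leave 3 points inside the interval.

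**Primary trial, 2 points, alpha 0.025, 15% loss.**

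| Comparison | Randomised | Power, SD 8 | Power, SD 7 |
|---|---|---|---|
| Standard v synthetic mesh | 253+178 = 431 v 256+181 = 437 | 88% | 95% |
| Standard v biological mesh | 253+116 = 369 v 255+114 = 369 | 81% | 91% |

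**The case against.** The best defence is that this section is a design-stage record. It is written in the language of expectation, it matches Protocol 2.7.2, and its arithmetic is correct. The shortfall is also not hidden. Protocol 2.7.3 gives the reason (about 16% of women met the same-compartment definition, against 30% assumed), section 7.2 records that the oversight committees and the funder approved the extension, and the SAP prints the actual counts. No analysis depends on the power paragraph, and the planned 95% confidence intervals will show how imprecise the secondary trial is.

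Most of this stands as mitigation. It rules out reading the planning calculation as wrong, or the shortfall as concealed. It does not remove the fault. What is disclosed is a headcount, not what that headcount can detect, and the SAP updated its tables and randomisation menus while leaving this section unlabelled.

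A second objection is that 19% and 33% are pessimistic, because SD 8 is described as conservative and the planned model adjusts for baseline. That is fair as to precision. The documents give no baseline correlation, so the gain cannot be quantified from them. As an assumption only, dividing the SD by 1/√(1 − r²) raises power to 25% (kit) and 43% (inlay) at r = 0.5, and to 37% and 60% at r = 0.7. Combining r = 0.7 with SD 7, alpha 0.05 and no loss gives 66% and 87%. No combination tried reaches 90%.

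A reader might also infer that the primary trial is materially underpowered. The documents do not support that: its shortfall depends on an unadjusted analysis with SD 8, and with the SD of 7 in Appendix IV both comparisons exceed 90%.

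**Conclusion.** The concern holds for the secondary trial, as a statement that was not updated rather than an arithmetic error. The SAP attributes 90% power for 3 points to a trial that, with the numbers in its own Table 3, has about 33% (mesh inlay) and 19% (mesh kit). Those two values rest on SD 8, two-sided alpha 0.025, 15% loss, no covariate adjustment and the combined-strata comparison for the inlay. The more favourable SD and alpha found elsewhere in the documents lift the range only to about 25% to 53%, before an adjustment gain of unknown size. The conclusion that power is far below 90% is therefore firmer than any single percentage.

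The primary trial's fall from 1450 to 1353 is a minor matter.

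**What to change.** - Keep the SAP sample size section and Protocol 2.7.2, but label them as the original design calculation. They should not be replaced, because they record how the targets were set.
- Add to the SAP, with a cross-reference from Protocol 2.7.3, the numbers actually randomised for each comparison.
- For each secondary-trial comparison, give the power, the detectable difference or the expected confidence-interval width, with SD, alpha, loss and adjustment stated. On the SAP's planning assumptions the detectable differences are about 5.9 points (inlay) and 7.8 points (kit).
- State that a non-significant secondary-trial result does not rule out a 3-point difference and should be read from its confidence interval.
- Optionally, give the primary-trial power under both SDs (88% and 81% with SD 8; 95% and 91% with SD 7).

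This is a wording change only, with no extra recruitment and no change to the analysis. The one cost is a less favourable stated power.
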